3.1 Responsibility

All tables, graphics and listings, and the statistical analysis will be produced by *CRO Dr. med. Kottmann GmbH & Co. KG*. The reconditioning / coding of diseases and drugs will be conducted by *Implandata Ophthalmic Products*.

3.2 Statistical Analysis Plan (SAP)

The Statistical Analysis Plan (SAP) will be finalized prior to data base lock. The SAP will incorporate all CIP amendments prepared for the study. In case of an amendment to the CIP after the SAP finalization date, an amendment to this SAP may be written.

The SAP will be produced and signed by CRO Dr. med. Kottmann GmbH & Co. KG and approved in writing by the sponsor.

3.3 Statistical analyses in SAS

All tables, graphics and statistical analyses will be performed using the statistical software SAS®, version 9.4.

3.4 Tables and graphics

The pertinent population of a table / graphic will be mentioned in the header.

3.5 Descriptive statistics

Descriptive statistics calculated for continuous variables will be

- number of patients
- number of valid patients
- mean
- standard deviation
- minimum
- maximum
- median
- percentiles (if indicated)

All continuous parameter will be tested for normal distribution by using Shapiro-Wilk-Test.

For categorical variables

- number of patients
- number of valid and/or missing values
- absolute frequencies (n)
- relative frequencies (%)

3.6 General missing data handling

In tables of continuous and categorial data the number of cases and the number of valid cases will be reported. The missing values will not be included in the calculation of percentages except when it appears reasonable on occasion.

If the calculation of periods requires the full date format dd-mm-yyyy, missing entries will be set to the first possible day of the month for a missing day. In case of a missing month, the first possible month of a year will be set.

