7.3 Risks and anticipated adverse device effects to be assessed

Information will be collected on all AEs and ADEs to allow assessment of the safety of implantation and use of the ARGOS-SC sensor in humans undergoing non-penetrating glaucoma surgery. Particular attention will be paid to ophthalmic AEs, for which increased risks are considered possible. However, because these AEs are common in this patient population, an independent assessment of their relationship to the ARGOS-SC sensor implant will not be possible. Possible adverse device effects will be subject to evaluations of the DSMB. Incidence, nature and severity will be compared to literature of standalone NPGS. AEs of particular interest include:

• Perforation/Rupture of the trabeculo-descement's membrane (TDM)

- Anterior chamber inflammation
- Hypotony (IOP < 5 mmHg for more than one month or hypotony maculopathy (e.g. with signs of maculopathy))
- Shallow anterior chamber
- Suprachoroidal hemorrhage
- Choroidal detachment
- Retinal detachment
- Hyphema
- Iris incarceration in TDM
- Temporary visual impairment as a secondary effect caused by the adverse events described above

Procedures that are anticipated in the general patient population in the follow-up period include:

- 360°-suture removal after canaloplasty
- Nd:YAG membranectomy
- Nd:YAG goniopuncture
- Nd:YAG iridotomy
- Retinal detachment repair
- Transcleral cyclophotocoagulation
- Vitrectomy with epiretinal membrane peeling
- Choroidal drainage
- Anterior chamber infusion with or without recombinant tissue plasminogen activator
- Re-suturing of the scleral flap
- Subconjunctival injection of dexamethasone
- Inserting a therapeutic soft contact-lens

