9.1.3 Safety Analysis

The incidence and nature of adverse events observed within the safety population will be analyzed by descriptive and explorative statistical methods.

Safety will be described in detail by frequency, seriousness, severity, nature and duration of events. Number of adverse events as well as the number and relative frequency of patients reporting adverse events will be tabulated by system organ class and preferred terms. The same table will be prepared for serious adverse events. In addition, the number and relative frequency of patients reporting adverse events will be tabulated by system organ class and preferred terms in dependence on the worst severity and worst causal relationship. Furthermore, number of adverse device effects as well as the number and frequency of patients reporting adverse device effects will be tabulated by system organ class and preferred terms and not by event description as stated in the protocol.

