2.8.4 Further study variables

- Inclusion criteria at Screening
- Exclusion criteria at Screening
- Demographic data at Screening
- Educational level at Screening
- Medical history at Screening
- · Glaucoma anamnesis at Screening
- Previous glaucoma medication (stopped before implantation) (Mock-up Table 3a)
- Concomitant glaucoma medication from V01 V09 (Mock-up Table 3b)
- Other previous medication (stopped before implantation)
- Other concomitant medication from V01 V09
- Pregnancy test (for female subjects of childbearing potential) at Screening and before surgery
- Surgery related data (study eye, examination prior surgery, ARGOS-SC implantation, Intraocular lens implantation, complications)
- Visual Function Questionnaire (VFQ-25) at Screening and visit V06, V07, and V09

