2.9.2 Secondary endpoints

Safety:

- Number of patients experiencing a device-related SAE (SADE) at any time during implantation and in the first 12 months (day 0 to day 360) following it.
- Incidence, nature, severity and seriousness of observed adverse events (AE) and adverse device events (ADE) at any time during implantation and in the 12 months following it.

Performance:

- Repeatability of the ARGOS-SC measurement.
- Comparison of OPA measurements with the repeatability of the ARGOS-SC measurement
- Incidence, nature and seriousness of observed device malfunctions during implantation and in throughout a 12 months follow-up period.

Utility:

- User acceptance of the ARGOS-SC implantation procedure by means of evaluation of implantation procedure questionnaires (surgeon)
- User acceptance of the ARGOS-SC system at the investigational site by means of evaluation of patient acceptance questionnaires (by investigators)
- User acceptance of the ARGOS-SC system at home by means of evaluation of patient acceptance questionnaires (patients)

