4.1.2 Methods for handling missing data

Missing data will not be replaced.

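### SAP 3.6 applies one earliest-date rule to incomplete start and end dates alike, so event durations are biased down or up depending on which date is incomplete

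*SAP*

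**What the plan says.** SAP 3.6 makes its date rule conditional: "If the calculation of periods requires the full date format dd-mm-yyyy", then "missing entries will be set to the first possible day of the month for a missing day". It continues: "In case of a missing month, the first possible month of a year will be set". The section draws no distinction between start and end dates. It sets no lower bound at event start, consent or implantation, and gives no rule for a negative period. 'First possible' could mean the 1st of the month (or January), or the earliest date compatible with the other known dates.

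SAP 4.1.2 states, without an exception for dates, "Missing data will not be replaced".

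Protocol 9.1.3 makes duration a planned output: "Safety will be described in detail by frequency, seriousness, severity, nature and duration of events". Protocol 11.3 has start and end date and time recorded for each event. SAP 4.6.2, which lists the adverse event tabulations, does not mention duration.

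**The concern.** An earliest-date rule acts in opposite directions on the two ends of an interval. On an end date it yields the shortest duration compatible with the data, or an impossible negative one. On a start date it yields the longest. Each affected duration is then wrong by an amount set by which field was left incomplete, not by anything clinical. In a first-in-human device study, the length of an adverse event is part of how its burden is judged.

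A second question is where a date falls relative to surgery. The safety endpoint in SAP 2.9.2 covers implantation and the period "in the first 12 months (day 0 to day 360) following it", and SAP 2.8.4 and 4.6.3 separate glaucoma drugs stopped before implantation from those given during V01 to V09. If the same rule dates these records, an event or drug stop known only to the month of surgery could be placed before surgery.

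**Working it through.** The plan states no figure that depends on this rule, so there is none to reproduce. The check applies the rule as the 1st of the month (and January for a missing month) to every date in a 365-day year, assuming start and implantation dates are uniform over the year.

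**1. Shift of one date, day missing.** A date on day d moves back d − 1 days. The shifts sum to 465 in a 31-day month (0 to 30), 435 in a 30-day month (0 to 29) and 378 in a 28-day February (0 to 27).

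- Total: 7 × 465 + 4 × 435 + 378 = 5,373.
- Mean: 5,373 / 365 = 14.7 days. The maximum is 30 in a 31-day month and 29 in a 30-day month.
- Day and month both missing: mean of 0 to 364 = 182 days, maximum 364.

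**2. Effect on duration, day missing.** End only: true length − 14.7 on average. Start only: true length + 14.7. Both: the errors cancel on average.

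| True length (days) | End day missing: mean | End day missing: negative | Start day missing: mean | Both missing: mean |
|---|---|---|---|---|
| 7 | −7.7 | 74% | 21.7 | 7.0 |
| 14 | −0.7 | 51% | 28.7 | 14.0 |
| 30 | 15.3 | 0% | 44.7 | 30.0 |

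Check of the 74%: a 7-day event goes negative when it starts after the 1st and ends in the same month, which is n − 8 start days in a month of n days. That gives (7 × 23 + 4 × 22 + 20) / 365 = 269 / 365 = 0.737.

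The zero average in the last column hides individual errors: with both days missing, an event that stays within one month is given 0 days.

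**3. Bounded reading.** If the imputed end date may not precede the start date, negative durations disappear. An incomplete end date still receives the shortest compatible duration.

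**4. Position relative to implantation, if the rule is used for that.** Take the true date as uniform over days 0 to W after implantation, with the day missing. For implantation on day d > 1 of a month of n days, the n − d + 1 dates left in that month all move before implantation. Summed over the year this is again 5,373.

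- W = 30: 5,373 / (365 × 31) = 47%.
- W = 90: 5,373 / (365 × 91) = 16%.
- W = 360: 5,373 / (365 × 361) = 4%.

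With day and month both missing, the shares are 96%, 87% and 50%. For example, with implantation on 17 June, an event dated only to June becomes 1 June, day −16. If dates are bounded at implantation, none moves before it.

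**5. A duration threshold, for illustration.** Protocol 7.3 defines hypotony of interest partly by lasting more than one month. An episode from 10 May to 19 June lasts 40 days; with the end recorded only as June it computes to 22 days (10 May to 1 June). A 45-day episode computes to 30 days or fewer when its true end falls on day 16 or later: (7 × 16 + 4 × 15 + 13) / 365 = 185 / 365 = 51%.

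**The case against.** The best defence is that few dates will be incomplete. Protocol 10.3 has data management query missing or questionable entries, and all queries must be answered before any analysis. The study is prospective, with 24 patients and event dates and times on the CRF. This stands as a limit on how many records are affected. It does not correct the rule for the records that remain, which are the only ones it governs.

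It is also fair that the safety analysis is descriptive and that SAP 4.6.2 lists no duration table. Protocol 9.1.3 nevertheless plans one, and SAP 3.6 is the only rule for computing it.

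A reader might infer more than the documents support:

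- **That every error favours the device.** Incomplete start dates lengthen durations by the same average.
- **That the SADE endpoint is undercounted.** It counts patients and needs no duration. Relatedness is an investigator's causality grade (Protocol 11.3.3), and SAP 4.6.2 applies no date filter.
- **That hypotony cases would be lost.** Nothing says this status is recalculated from imputed dates, and hypotony maculopathy qualifies separately. Step 5 shows only what would happen if it were.
- **That drugs would be moved into the table of previous medication.** The rule is conditional on a period calculation, and the SAP does not say that it decides the previous or concomitant label. Medication is also recorded at every visit.
- **That events are shifted to before surgery.** This needs both the unbounded reading and use of the rule for event timing; the SAP states neither.

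**Conclusion.** The point holds in a limited form. SAP 3.6 states a rule that gives wrong durations: about 14.7 days too short on average when the end day is missing, about 14.7 days too long when the start day is missing, and often negative for short events if 'first possible' means the 1st of the month. The minimum-duration result for incomplete end dates holds on either reading. The figures assume dates uniform over the year.

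Placement before implantation is a conditional risk, to be settled by stating the rule's scope. The number of affected records cannot be computed, because the documents give no frequency of incomplete dates. The primary agreement endpoint uses clinic IOP values by visit and is untouched. This is an inexpensive correction to make before the SAP is finalised, which SAP 3.2 places ahead of database lock.

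**What to change.** Replace the date rule in SAP 3.6 with:

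1. **Incomplete end date:** the last day of the known month or year, capped at last contact and never before the start date.
2. **Incomplete start date:** the first day of the known period. If that period includes implantation and the CRF does not show onset before surgery, use the implantation date. Never set it after a known end date. The last condition is needed because Protocol 8.3.17 and 11.3 record events from consent (8.3.13.4 says from implantation), so some may have ended before surgery.
3. **Drug stops:** a drug whose incomplete stop date could fall on or after implantation is counted as concomitant.
4. **Consistency:** except dates from SAP 4.1.2, and flag every imputed date in the listings.

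The cost is a few sentences and a few lines of code, with no new data. Some durations and concomitant-drug counts become slightly less favourable. A duration with an imputed end date becomes an upper bound: before the cap, a missing end day is overstated by the same 14.7 days on average, since the days left in the month sum to the same 5,373. The report should label such durations as upper bounds.

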3.7 Analysis populations

The following populations will be defined for analysis:

Safety-Analysis Set (SAF): The safety analysis set will comprise all patients
that gave written informed consent to participate in the study and the ARGOS-SC
pressure sensor implantation was attempted, defined as introduction of the
ARGOS-SC pressure sensor into the study eye, whether or not the implantation
was successful.

Per protocol set (PP)

The Per Protocol Set (PP) will comprise all subjects in whom an ARGOS-SC pressure sensor was successfully implanted and for whom the full data set including IOP measurements made in the clinic and safety data according to protocol are available until 3 months (V06) after surgery. Because IOP measurements conducted outside the clinic will be made at varying times under varying conditions, they are not anticipated to be comparable to those made in the clinic and will not be included in the Per-Protocol evaluation of agreement.

Performance analyses will be based on the SAF and PP, the safety analyses on the SAF.

3.8 Major protocol violations

In general, major protocol violations are

- Substantial violation of inclusion or exclusion criteria
- Missing primary or secondary performance parameters
- Extensive time window violation

4 Data Analysis

4.1 General methodological considerations

4.1.1 Methods for handling dropouts

All patients will be analysed as far as documented.

4.1.2 Methods for handling missing data

Missing data will not be replaced.

4.1.3 Methods for handling outliers

Outliers which cannot be justified will be excluded from the analysis.

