8.1.2 Description of the measures to be taken to minimize or avoid bias

No randomization or blinding/masking procedures will be used in this study. To avoid bias resulting from patient selection, all consecutive patients who potentially meet the eligibility requirements will be informed of the study and asked to participate. Those agreeing will undergo the informed consent procedure and if they consent, will be screened. All eligible patients will be enrolled.

There will be no control group for safety events. Incidence, nature and severity will be compared to literature of standalone NPGS. To allow assessment of performance, measurements of IOP with the ARGOS-SC sensor will be compared to those obtained with the standard GAT method and Pascal DCT at the same time point. To prevent possible influence of prior knowledge of the IOP value obtained with the ARGOS-SC, which is objectively displayed, measurements will always be made first with GAT/DCT. Data on all device deficiencies will be recorded.

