9.5 Pass/fail criteria to be applied to the results of the clinical investigation

This investigation will be considered a success if no more than one of the 24 patients experiencing SADEs during the follow-up period (SADEs evaluated by DSMB) and if 70% of the measurements agree between +/- 5 mmHg (limits of agreement from GAT and ARGOS-SC measurements are between +/- 5 mmHg).

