9.10 Treatment of missing, unused and spurious data, including drop-outs and withdrawals

All data of the patients will be used as available. All analyses will be performed on observed cases only. Missing data will not be replaced. Implausible values will be only excluded from the analysis if reasonable. The reason for exclusion will be given in the footer of the table or description of the figure. Patients terminating the trial prematurely due to whatever reason will be evaluated like any patient completing the trial as per protocol, within the analysis sets they qualify for.

Subjects who dropped out during a scheduled visit will be counted for that visit.

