4.6 Analysis of endpoints

4.6.1 Performance endpoints

The evaluation uses the following methods to analyze the agreement between two different measurement methods

Bland-Altman Plot:

Bland and Altman introduced the Bland-Altman plot to describe agreement between two quantitative measurements by constructing limits of agreement. These statistical limits are calculated by using the mean and the standard deviation (s) of the differences between two measurements. To check the assumptions of normality of differences and other characteristics, they used a graphical approach.

The resulting graph is a scatter plot XY, in which the Y axis shows the difference between the two paired measurements (x-y) and the X axis represents the average of these measures ((x+y)/2). In other words, the difference of the two paired measurements is plotted against the mean of the two measurements. Bland-Altman recommended that 95% of the data points should lie within \pm 2s of the mean difference. This is the most common way to plot the Bland-Altman method.

The bias is computed as the value determined by one method minus the value determined by the other method. If one method is sometimes higher, and sometimes the other method is higher, the average of the differences will be close to zero. If it is not close to zero, this indicates that the two assay methods are systematically producing different results.

Concordance correlation coefficient

Concordance correlation coefficient (r_{ccc}) measures the agreement between two variables X and Y. Lawrence Lin has defined the form of the concordance correlation r_{ccc} as^[1]

$$r_{ccc} = 2 r s_x s_y / ((s_x^2 + s_y^2) + (m_x - m_y)^2)$$

with

 $r = s_{xy}/(s_x s_y)$ (Pearson correlation coefficient)

 m_x = mean of X

 $m_y = mean of Y$

 s_x = standard deviation of X

 s_y = standard deviation of Y

 s_{xy} = covariance of x and Y

The concordance correlation r_{ccc} has an range of -1 to 1. Values near +1 indicate strong concordance between x and y, values near -1 indicate strong discordance and values near zero indicate no concordance. There is no clear-cut agreement as to how to interpret the values, although one approach is to interpret Lin's r_{ccc} as for Pearson's correlation coefficient (e.g. values less than .20 are poor, while values greater than .80 are excellent).

The following values will be calculated:

- Calculation of the average of the (up to) 3 IOP measurements using GAT (GAT_{mean})

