4.7 Other topics of data analysis: Coding

- Reconditioning / coding of adverse events, diagnoses, and concomitant diseases
 will be conducted by *Implandata Ophthalmic Products*
- Coding of concomitant medication by ingredients will be conducted by *Implandata* Ophthalmic Products

5 Mock-up tables and figures

Table 1(dummy data)

able 1(dummy data)						
Demographic data						
Gender	N	50				
	male	20 (40.0%)				
	female	30 (60.0%)				
Age [years]	N					
	Mean					
	Mean [95% CI]					
	Standard dev.					
	25Percentile					
	Median					
	75Percentile					
	Minimum					
	Maximum					

Table 2

IOP measurements: GAT and ARGOS-SC										
		Visit V02	Visit V03	Visit V04	Visit V05	Visit V06				
GAT	N	22	22	21	22	17				
	Mean	7.36	9.82	12.81	13.05	12.24				
	Mean [95% CI]	5.03 9.70	7.19 12.45	10.45 15.17	10.93 15.16	10.13 14.34				
	SD	5.26	5.93	5.18	4.78	4.10				
	25Percentile	3.00	6.00	7.00	10.00	11.00				
	Median	5.50	8.50	13.00	13.00	12.00				
	75Percentile	9.00	12.00	17.00	17.00	14.00				
	Minimum	2.0	2.0	6.0	4.0	4.0				
	Maximum	24.0	27.0	22.0	24.0	19.0				
ARGOS-SC	N	21	21	20	22	17				
	Mean	8.24	10.52	15.05	14.95	12.65				
	Mean [95% CI]	5.77 10.7	8.23 12.82	11.53 18.57	12.10 17.81	9.25 16.04				
	SD	5.42	5.05	7.51	6.45	6.60				
	25Percentile	5.00	7.00	8.50	11.00	9.00				
	Median	7.00	9.00	15.50	14.50	12.00				
	75Percentile	11.00	14.00	20.00	18.00	14.00				
	Minimum	2.0	3.0	4.0	4.0	5.0				
	Maximum	24.0	22.0	31.0	29.0	33.0				
Difference	N	21	21	20	22	17				
	Mean	0.81	0.71	2.20	1.91	0.41				
	Mean [95% CI]	-0.17 1.79	-0.86 2.29	0.31 4.09	0.41 3.41	-1.84 2.67				
	SD	2.16	3.47	4.05	3.38	4.39				
	25Percentile	0.00	-2.00	-0.50	0.00	-2.00				
	Median	1.00	1.00	2.50	2.00	0.00				
	75Percentile	2.00	4.00	3.50	5.00	1.00				
	Minimum	-2.0	-7.0	-5.0	-4.0	-4.0				
	Maximum	6.0	6.0	13.0	7.0	15.0				

IOP measur	IOP measurements: GAT and ARGOS-SC								
		Visit V02	Visit V03	Visit V04	Visit V05	Visit V06			
Absolute	N	21	21	20	22	17			
difference	≤ 5 mmHg	20 (95.2%)	18 (85.7%)	18 (90.0%)	17 (77.3%)	16 (94.1%)			
	> 5 mmHg	1 (4.8%)	3 (14.3%)	2 (10.0%)	5 (22.7%)	1 (5.9%)			
	rccc	0.91	0.80	0.76	0.78	0.68			

[figure not shown]

Table 3a

Previous medication due to glaucoma					
Drug / ingredients					
Brinzolamides					
Total	N (%)				

Table 3b

Concomitant medication due to glaucoma								
Drug / ingredients Begin + - End								
Brimonidine	10	15	3	22				
Brinzolamides								
Total								

Begin: administration at V01
+ started during the study

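### SAP 4.1.3 deletes unexplained, undefined outliers by default, reversing protocol 9.10 in a study whose primary endpoint is agreement

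*SAP*

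**What the plan says.** SAP 4.1.3 consists of one sentence: "Outliers which cannot be justified will be excluded from the analysis". It gives no threshold, no unit of application, no decision-maker and no analysis with the excluded values restored.

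Protocol 9.10 starts from inclusion: "All data of the patients will be used as available". It then allows a limited exception, "Implausible values will be only excluded from the analysis if reasonable", and attaches a reporting duty: "The reason for exclusion will be given in the footer of the table or description of the figure".

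SAP 4.6.1 works at several levels. It first averages within a visit (for GAT, "Calculation of the average of the (up to) 3 IOP measurements using GAT"; likewise for the sensor), then forms the difference of the two means. From these it derives the Bland-Altman display, the concordance coefficient and the share of absolute differences up to 5 mmHg. Protocol 9.5 requires 70% of measurements to agree within 5 mmHg and adds that the "limits of agreement from GAT and ARGOS-SC measurements are between +/- 5 mmHg". On masking, protocol 8.1.2 says: "No randomization or blinding/masking procedures will be used in this study".

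**The concern.** Under protocol 9.10 a value stays unless there is a reason to remove it. Under SAP 4.1.3 an outlier goes unless there is a reason to keep it. A large but physiologically possible sensor–GAT difference with no known cause stays under the first rule and can be deleted under the second. In a method-comparison study that difference is the disagreement being measured.

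All three primary outputs depend on it: limits of agreement, concordance coefficient and share within 5 mmHg. Deleting large differences improves all three in the device's favour. Deleting extreme but concordant readings can do the opposite to the concordance coefficient, because it removes between-patient spread. With no definition of an outlier and no requirement to decide without sight of the paired value, the deleted pairs can be chosen once the differences are known. A sensor that occasionally misreads badly could then look more accurate than it is.

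**Working it through.** **Inputs.** The n, mean, SD, quartiles and extremes come from mock-up Table 2 (SAP section 5). They serve only as an illustration, not as results.

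**Reproducing the table.** The shares within 5 mmHg are 20/21, 18/21, 18/20, 17/22 and 16/17, that is 95.2, 85.7, 90.0, 77.3 and 94.1%, as printed. Pooled: (20+18+18+17+16)/(21+21+20+22+17) = 89/101 = 88.1%. Concordance can be rebuilt from the printed SDs with s_xy = (s_x² + s_y² − s_d²)/2 and r_ccc = 2s_xy/(s_x² + s_y² + (m_x − m_y)²). For V06: s_xy = (6.60² + 4.10² − 4.39²)/2 = 20.55, so r_ccc = 41.10/(60.37 + 0.41²) = 0.68. All five visits match within rounding (0.91, 0.80, 0.76, 0.78, 0.68).

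**Which pairs go depends on the definition.** Three ordinary rules, none of them named in the documents:

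- 3 SD on differences: V06 maximum z = (15 − 0.41)/4.39 = 3.3, removed; V04 maximum z = (13 − 2.20)/4.05 = 2.7, kept.
- 1.5 IQR on differences: upper fences are 5 (V02), 9.5 (V04) and 5.5 (V06), so at least the 6, 13 and 15 mmHg pairs go. V03 and V05 have nothing outside their fences. Removing those three moves the pooled share from 89/101 to 89/98 = 90.8%.
- 3 SD on each device's own values: flags GAT 24 at V02, z = (24 − 7.36)/5.26 = 3.2, and ARGOS-SC 33 at V06, z = (33 − 12.65)/6.60 = 3.1.

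**Effect of deleting the largest difference.** With S = n·m and Q = (n−1)s² + n·m², remove x and recompute. For V06: S = 6.97 and Q = 311.21. The new mean is (6.97 − 15)/16 = −0.50. The new variance is (311.21 − 225 − 16 × 0.50²)/15 = 5.48, so SD = 2.34. Limits are mean ± 1.96 SD.

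| Visit | Pair removed | SD | Limits before | Limits after |
|---|---|---|---|---|
| V02 | +6 | 2.16 → 1.85 | −3.42 / +5.04 | −3.08 / +4.18 |
| V04 | +13 | 4.05 → 3.24 | −5.7 / +10.1 | −4.7 / +8.0 |
| V06 | +15 | 4.39 → 2.34 | −8.2 / +9.0 | −5.1 / +4.1 |

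At V02 a single deletion brings the limits inside the ±5 mmHg named in protocol 9.5. At V06 the share rises from 16/17 to 16/16. If the V06 pair is ARGOS-SC 33 with GAT 18 (33 − 15), r_ccc rises from 0.68 to about 0.83.

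**Opposite direction.** If the two V02 maxima (24 and 24) belong to one patient, which is an assumption, deleting that concordant pair lowers r_ccc from 0.91 to about 0.82–0.83.

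**Pass/fail.** In the mock-up the lowest visit is 77.3% with every pair kept, so no deletion changes the 70% result. Nearer the threshold it can. Assume complete data, 24 × 8 = 192 pairs, with only disagreeing pairs deleted. The smallest d with k/(192 − d) ≥ 0.70 is:

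| Agreeing k | Share | Disagreeing | d needed | Share after |
|---|---|---|---|---|
| 131 | 68.2% | 61 | 5 | 131/187 = 70.1% |
| 127 | 66.1% | 65 | 11 | 127/181 = 70.2% |
| 125 | 65.1% | 67 | 14 | 125/178 = 70.2% |

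If the true share were 65%, the chance of observing at least 70% in 192 independent pairs is 7.0% with no deletion. It is 15.5% if up to 2% of pairs (all disagreeing) may be dropped, and 34.4% if up to 5% may be. Independence is a simplification, since pairs cluster within patients.

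**The case against.** The best defence is that the two documents are closer than they look. Protocol 9.10 also permits exclusion and does not define its own term, and the SAP sentence could be read as covering values that remain implausible after checking. Protocol 10.3 has out-of-range or questionable data queried and resolved before lock. The duty in 9.10 to print reasons is not cancelled by the SAP's silence, and 9.8 requires significant deviations from the statistical plan to be reported. Mock-up Table 2 keeps its 13 and 15 mmHg differences. GAT and DCT are read before the sensor, and a third reading is required when two differ by more than 2 mmHg. The study is exploratory with 24 patients, and the 70% effect is hypothetical.

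Part of this stands. What is reversed is the default, not a total ban on exclusion. The duty to give reasons survives in the protocol. The numbers are illustrations, and the SAP reports by visit rather than on a pooled 192.

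The rest does not remove the problem. Queries settle whether a value was recorded correctly; they set no exclusion rule. Printing a reason discloses a deletion but does not prevent it, and a deletion made under 4.1.3 follows the SAP, so 9.8 need not be triggered. Reading GAT first protects the measurement, not later data cleaning. A mock-up that retains extreme pairs does not override the written rule. An exploratory label sits badly beside an explicit pass/fail criterion.

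**Conclusion.** The concern holds. This is a wrong rule rather than a missing detail: followed as written, it removes unexplained disagreement from a study designed to measure disagreement, and it conflicts with the protocol's default. In the illustration, one deleted pair roughly halves the SD of the differences at one visit and brings the limits inside ±5 mmHg at another, and which pairs go depends on a definition that nobody has stated. The 70% criterion is at risk only if the true share lies near 70%; the figures for that case assume 192 complete pairs and deletion of disagreeing pairs only. The direction is not fixed, because removing concordant extremes can lower the concordance coefficient. The rule should be corrected before the primary analysis is run.

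**What to change.** Replace SAP 4.1.3 with a paragraph to this effect:

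> The primary agreement analysis includes every scheduled GAT and ARGOS-SC series reading from V02 to V09, and every DCT series reading with its paired ARGOS-SC series from V05 to V09 where DCT is available, for patients in the relevant analysis set. A single reading is removed, before visit means are formed, only for a documented measurement or recording error (for example a device error flag, the wrong eye or a transcription error). The decision is made without reference to the paired value or the difference. Each removal and its reason is reported as protocol 9.10 requires. Extremeness alone is not a ground for removal. Any analysis without extreme values is a labelled sensitivity analysis.

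This is narrower than protocol 9.10 read literally, but it gives concrete content to that section's test of reasonableness and keeps its default. The cost is one SAP paragraph and a data review in which the person judging a reading sees one method at a time. No new data are needed. The reported limits of agreement may be wider.
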